- Treatment with oral immunosuppressants (including cyclosporine, methotrexate, azathioprine, mycophenolate mofetil), alitretinoin or phototherapy within 4 weeks of baseline visit.
- Treatment with an investigational drug within 8 weeks (or 5 half-lives) of baseline.
- Active chronic infection requiring the use of a systemic antibiotic within 2 weeks before study start.
- Known or suspected history of immunosuppression, including history of invasive opportunistic infections (e.g., tuberculosis, histoplasmosis, listeriosis, coccidioidomycosis, pneumocystis, aspergillosis) despite infection resolution; or unusually frequent, recurrent, or prolonged infections, per investigator judgment.
- History of human immunodeficiency virus (HIV) infection or positive HIV serology at screening.
- Positive for hepatitis B surface antigen, hepatitis B core antibody, or hepatitis C antibody at the screening visit.
- Patients with known helminth infections.
- Pregnant or breastfeeding women, or women planning to become pregnant or breastfeed during the study.
 Women of childbearing potential who are sexually active and unwilling to use an adequate birth control method.

After confirmation of eligibility, patients are randomly allocated by a computer-generated randomization system in a 1:1 ratio to receive one of the following two treatment strategies:

- Dupilumab 300 mg for subcutaneous administration. Two initial injections of 300 mg dupilumab will be administered, followed by one injection of 300 mg every 2 weeks until week 14.
- Placebo with the same administration procedure.

The randomization is performed in a stratified manner based on the presence or not of a personal history of atopic dermatitis, as it is expected to be the major factor potentially influencing the primary endpoint. Baseline severity is not expected to influence the primary endpoint, as the relative change in mTLSS is not anticipated to be influenced by disease severity.

After randomization, study treatment is begun as soon as possible.

Some treatments/procedures are prohibited during the study as either they may influence disease outcome or may pose a safety risk for patients. Treatment with the following concomitant medications is prohibited during the study

- Treatment with immunomodulating biologics.
- Treatment with an investigational drug (other than dupilumab).

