5.3. DETERMINATION OF SAMPLE SIZE

The sample size is determined by the primary objective of the study, that is, to compare the percentage change in mTLSS score from baseline to Week 16.

His calculations are based on a clinically meaningful absolute difference between groups in the mean percentage change in mTLSS score from baseline to Week 16 of -25% (greater percentage decrease expected in dupilumab compared with placebo). Assuming a standard deviation of 40% in both groups, sample size of 84 patients (42 by group) will achieve over 80% power to detect such a difference with a significance level (type-I error) of 0.05 using a two-sided two-sample t-test (7).

To account for potential non-evaluable patients estimated to 10%, a total of 94 patients will have to be randomized.

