6.2. INFERENTIAL STATISTICS

The primary objective of study is to demonstrate that dupilumab is more effective than placebo for the treatment of patients with moderate to severe CHE who are resistant or intolerant to highly potent topical corticosteroids as determined by the evolution at week 16 of the mTLSS since baseline. The study is sized on the basis of the primary objective only. The study uses a single primary endpoint and has a confirmatory statistical strategy that pre-specifies just one single null hypothesis relating to the primary endpoint and no formal interim analysis.

The primary analysis of the primary endpoint, which forms the basis for the sample size justification, involves comparing the percentage change from baseline to week 16 of the severity score mTLSS between the experimental arm (dupilumab) and the control arm (Placebo) using a covariance analysis. This analysis includes the group, the stratification factor (personal history of atopy), the baseline mTLSS score and the interaction between the stratification factor and the treatment arm as covariables. The treatment effect is tested at a 5% significance level.

The null hypothesis H_0 is that the percentage change in experimental arm is the same as the percentage change in control arm. The alternative hypothesis H_a is that percentage change in experimental arm differs from percentage change in control arm.

All other analyses of the other efficacy endpoints, are intended to yield supportive evidence related to the primary objective and to provide additional characterization of treatment effects, and no claims are intended. Confidence Intervals (CIs) and statistical tests, if any, that are part of these analyses are of exploratory nature and will be performed without any adjustment of type I error. They will be two-sided and performed each at the 0.05 significance level, unless otherwise specified.

Similarly, analyses on safety endpoints are used in an exploratory manner. CIs and statistical tests, if any, will be two-sided and performed each without any adjustment for multiplicity at the 0.05 significance level.

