13.1.2. Primary analysis

Primary analysis of the primary efficacy endpoint will be carried out on the ITT population, using an adjusted approach controlling for those factors on which the randomization is stratified and on the value of the baseline endpoint.

Levels of factors on which the randomization is stratified will be derived from actual data - that is, last investigator eCRF data entry - to compensate for cases where erroneous stratification factor information were given at the time of randomization leading to randomization in a wrong stratum; see Section 8.1 for details of randomization irregularities.

Percentage change in mTLSS score from baseline to week 16 will be compared between Arm A and Arm B using a covariance analysis (ANCOVA) including the group, the stratification factor, the baseline mTLSS score, and the interaction between the treatment arm and the stratification factor as covariables. Initially, a bivariate test will be conducted between the variable to be explained (percentage change of mTLSS) and the treatment arm. The choice of the test will be based on classical criteria such as normality and homoscedasticity. Subsequently, an Analysis of Covariance (ANCOVA) will be performed. If the interaction is not significant ($p\geq0.05$), it will be excluded from the model. Otherwise, the analysis will be stratified based on the stratification factor.

Finally, we will verify if the conditions for applying ANCOVA are met by examining the distribution of the residuals graphically (normality and homoscedasticity).

In case all assumptions are not met, we will proceed with a linear regression using the same variables as the previous model but employing a more robust approach (10–12) that tolerates heteroscedasticity.

The null hypothesis H_0 is that percentage change in mTLSS score of Arm A is the same as percentage change in mTLSS score of Arm B after adjustment for stratification factor and the baseline score. The alternative hypothesis H_a is that percentage change in mTLSS score of Arm A differs as percentage change in mTLSS score of Arm B after adjustment for stratification factor and the baseline score.

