The percentage change based on the treatment arm will be presented as the difference between the percentage change in arm A and the percentage change in arm B after adjustment. It will be presented with its 95% confidence interval (95% CI) constructed using the estimator of the standard variance for ordinary least squares (OLS) regression if the aforementioned hypotheses are met. Otherwise, this confidence interval will be provided using the robust standard errors described by Eicker-Huber-White (10–12) for heteroskedastic models. Finally, the predicted values per treatment group and their difference will be presented with their 95% CI.

These data will be presented in a table such as the one below:

Percentage change in mTLSS	N	β Coefficient	β 95% CI	p-value
Treatment arm				
Placebo	n	0		
Dupilumab	n	eta_1	$(CI_1;CI_{1'})$	p_1
Randomization stratum				
Presence of a personal history of atopic dermatitis				
No	n	0		
Yes	n	eta_2	$(CI_2;CI_{2'})$	p_2
mTLSS score at inclusion	n	β_3	(CI ₃ ; CI _{3'})	p_3
Other qualitative parameter of interest				
Modality 1	n	0		
Modality 2	n	eta_4	$(CI_4;CI_{4^{\text{'}}})$	p_4
Modality 3	n	eta_5	$(CI_5;CI_{5'})$	p_5
Other quantitative parameter of interest	n	eta_6	$(CI_6;CI_{6'})$	p_6
R - squared	R^2			

Percentage change in mTLSS	Mean predicted values	95% CI
Treatment arm		
Placebo		(CI; CI)
Dupilumab		(CI; CI)
Dupilumab - Placebo		(CI; CI)

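### The standard error behind the primary p-value is chosen after a subjective look at unblinded residuals, and the robust form is not named; the effect on type I error is small and the fix is cheap

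*SAP*

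**What the plan says.** SAP section 6.2 sets up one confirmatory null hypothesis: "The treatment effect is tested at a 5% significance level". Section 13.1.2 specifies the ANCOVA on percentage change in mTLSS with arm, stratification factor, baseline mTLSS and, at first, the arm-by-stratum interaction. The residuals are then inspected graphically for normality and homoscedasticity. The consequence of a poor plot is: "In case all assumptions are not met, we will proceed with a linear regression using the same variables as the previous model", with an approach that tolerates heteroscedasticity.

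The paragraph on the confidence interval in the same section uses the OLS variance if the assumptions hold. If they do not: "Otherwise, this confidence interval will be provided using the robust standard errors described by Eicker-Huber-White". It cites the founding papers for this estimator and names no finite-sample version.

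Section 3 says allocation is released once the last patient has finished, the database is clean and the SAP is validated. The arm codes are therefore in hand when this model is fitted. Section 5.3 assumes equal spread: "Assuming a standard deviation of 40% in both groups".

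**The concern.** The error bar of the trial's only confirmatory test depends on how someone reads a plot, after treatment is known. The SAP gives no threshold, no masked reader, and no statement of which result stands if two readers differ. Two competent statisticians could follow the text and report different p-values from the same coefficient.

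Three details add to this.

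- **The fallback is not reproducible as written.** HC0, HC1, HC2 and HC3 are all Eicker-Huber-White forms. They differ noticeably at about 84 patients, and uncorrected HC0 is too small there.
- **The remedy does not match both triggers.** Robust errors address unequal variance. They do nothing specific for non-normal residuals, which the SAP also treats as a reason to switch.
- **Unequal spread is plausible.** Percentage change as defined in section 13.1.1 cannot fall below -100%, so an arm that improves more may vary less. The check may therefore come into play.

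The choice also carries over. The sensitivity analyses in section 13.1.3 and the continuous secondary endpoints in section 13.2 are described as similar analyses, so each could end with a different standard error.

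**Working it through.** **1. The plan's own figures.** Inputs from section 5.3: difference 25 points ("mean percentage change in mTLSS score from baseline to Week 16 of -25"), SD 40, "significance level (type-I error) of 0.05 using a two-sided two-sample t-test", and 10% non-evaluable. Section 5.1 gives 1:1 allocation.

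- Normal approximation: n per arm = 2(1.960 + 0.842)² × (40/25)² = 40.2, so 41.
- SE at 42 per arm = 40 × √(2/42) = 8.73. 25/8.73 = 2.864, giving power Φ(2.864 - 1.960) = 81.7%.
- Noncentral t: 42 per arm and 80.8% power.
- 84/0.90 = 93.3, so 94.

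The statement "sample size of 84 patients (42 by group) will achieve over 80% power" reproduces.

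**2. The competing variances.** Let c pick out the arm coefficient, a = c′(X′X)⁻¹X′, eᵢ be the residuals, hᵢ the leverages, N = 84 and k = 4 (intercept, arm, stratum, baseline).

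- OLS: c′(X′X)⁻¹c × Σeᵢ²/(N - k)
- HC0: Σaᵢ²eᵢ²
- HC1: HC0 × N/(N - k) = HC0 × 84/80 = 1.05 × HC0, so the SE is about 2.5% larger
- HC2: Σaᵢ²eᵢ²/(1 - hᵢ)
- HC3: Σaᵢ²eᵢ²/(1 - hᵢ)²

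The coefficient is the same throughout.

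**3. How unequal the evaluable arms can become.** Section 6.3.5 makes no imputation if week 16 is missing for less than 10% of randomized patients, and uses last available data above 10%. With 47/47 randomized, 9/94 = 9.6% stays below the threshold and 10/94 = 10.6% crosses it. The most lopsided split without imputation is therefore 38/47.

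**4. Closed-form check of OLS, ignoring covariates (SDs assumed).**

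- 38 patients with SD 50 and 47 with SD 25: pooled variance = (37 × 2500 + 46 × 625)/83 = 1460.8. OLS SE = √(1460.8 × (1/38 + 1/47)) = 8.34. True SE = √(2500/38 + 625/47) = 8.89. Ratio 0.938. The critical value 1.989 acts as 1.865, an error of about 6.2% (normal) to 6.6% (t).
- Losses in the other arm, 47 with SD 50 and 38 with SD 25: OLS SE 8.90 against true 8.34, ratio 1.066, an error of about 3.4-3.7%.
- 42/42 with the same SDs: both SEs are 8.63, so there is no distortion.

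**5. Simulation of the ANCOVA without interaction, no treatment effect.** Mainly 40,000 runs per setting, with additional 20,000-run checks. Assumed, not in the SAP: baseline mTLSS about N(11, 3.5) cut to 4-21; stratum prevalence 20-50%; arm SDs 40/40, 20/40 or 25/50, and 50/27 in additional runs; settings with variance depending on baseline and with skewed errors.

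| Rule | Type I error at nominal 5% |
|---|---|
| OLS always, 42/42 | 4.7-5.3% |
| HC0 always, 42/42 | 5.4-6.0% |
| Objective switch, OLS to HC1 (Breusch-Pagan p<0.05 as proxy for the plot) | about 5.0-5.5% |
| Smaller p of OLS and HC1, 42/42 | 5.1-5.8% |
| Smaller p of OLS and HC0, 42/42 | 5.5-6.1% |
| OLS, 38 (SD 50) / 47 (SD 25-27) | about 6.5-6.7% |
| HC2 always | about 5.0-5.5% |
| HC3 always | about 4.4-5.0% |

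Single settings fell slightly below these last two ranges (HC2 4.8%, HC3 4.2%). With 42/42, OLS and HC1 disagree on significance in 0.4-0.9% of null trials, and in about 1.0% of trials under the planned effect.

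**6. Power at 84 evaluable, difference 25.** SD 40/40: OLS 80.1%, HC2 80.1%, HC3 78.7%. SD 25/50: OLS 80.7%, HC2 80.7%, HC3 79.3%.

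**The case against.** The strongest reply is that the SAP gives a directional rule, OLS if the assumptions hold and robust otherwise, and that this rule nearly holds its level when applied objectively. That stands, and it limits the size of the point. What remains is that nothing makes the application objective, and the robust form is unnamed.

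Several stronger readings are tempting, and the documents do not support them.

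- **That the error reaches 7-8%.** OLS gives 7.2% at 36/48 evaluable and 8.2% at 36/47 with skewed errors. Those splits leave 10/94 = 10.6% and 11/94 = 11.7% missing. Section 6.3.5 then brings back patients who have an intermediate score, and the arms move towards 47/47. At 47/47 with the same unequal SDs, OLS gives 4.8-5.1%.
- **That the analyst may pick either p-value.** The fault is a subjective trigger, not a free choice. The smaller-p rows are a worst case, not the plan.
- **That it is open whether one failed assumption is enough.** The sentence on the switch is loosely worded, but the if/otherwise construction for the confidence interval largely settles it: any failure leads to the robust error.
- **That the SAP prescribes HC0.** It names the family and no version.
- **That a fixed robust error protects the 5% level.** The interaction rule in section 13.1.2 remains. If success in either stratum counts after a significant interaction (the SAP does not say), the error is about 6.8% with HC3 and 7.8-8.2% with OLS. The preliminary bivariate test, itself selected on normality and homoscedasticity, also remains.

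It can also be said that mandatory HC3 takes power just below the 80% target. That is correct, and it is a reason to prefer HC2 or to state the cost.

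**Conclusion.** The point holds as a minor one. Section 13.1.2 leaves the standard error, interval and p-value of the single confirmatory comparison to an unblinded judgement without a criterion, and the fallback cannot be reproduced from the text. The estimate of effect is untouched.

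With near-equal arms the cost is a few tenths of a percentage point, and at worst about one. It approaches 1.5-1.7 points only if OLS is retained when nearly all permitted losses fall in the arm with the larger SD; if they fall in the other arm, OLS is conservative. These sizes rest on assumed SDs, baseline distribution, stratum prevalence and loss patterns, and on a formal test standing in for the visual check.

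The reason to act is reproducibility at almost no cost, not a serious threat to the trial's conclusion.

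**What to change.** In section 13.1.2, state that the treatment coefficient from the primary ANCOVA is always reported with one named small-sample robust standard error and a t reference, for both the 95% CI and the p-value. There are two reasonable choices:

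- **HC2**, as the default: error about 5.0-5.5%, essentially no power loss.
- **HC3**, if a conservative test is preferred: error about 4.4-5.0%, at a cost of about 1.5 power points. Power is then just under 80% at 84 evaluable, and the SAP should say so.

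Report the OLS standard error as supportive. Keep the residual plots as description. Delete both the conditional switch of model and the conditional choice of variance for the confidence interval. Apply the same rule to the sensitivity analyses and to the secondary endpoints analysed in the same way.

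The change is SAP wording only and needs no new data or patients. The interaction rule and the preliminary bivariate test should be dealt with separately, and this change should not be described as securing the overall 5% level.

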13.1.3. Sensitivity analyses

To evaluate the robustness of the results of the primary analysis of the primary efficacy endpoint, three sensitivity analyses of the primary efficacy endpoint will be performed:

- A similar analysis will be carried out after using the multiple imputation method to deal with missing outcomes, as described in section 6.3.5.
- A similar analysis will be carried out without imputing the missing outcomes. Thus, only participants with complete data concerning outcomes at the visit 9 will be considered in the analysis.
- Finally, a similar analysis will be carried out on the PP population, as described in section 8.2.2.

13.2. SECONDARY EFFICACY ENDPOINTS

Secondary efficacy endpoints will be tested without adjusting for multiplicity. There will be no fixed order of endpoints as this study is not considered a confirmatory phase III study. Secondary analyses will be performed on the ITT population. Levels of factors on which the randomization is stratified will be derived from actual data - that is, last investigator eCRF data entry - to compensate for cases where erroneous stratification factor

information were given at the time of randomization leading to randomization in a wrong stratum; see Section 8.1 for details of randomization irregularities.

13.2.1. Investigator global assessment

Definition and derivation

The efficacy endpoint is based on IGA at the visit 9. The test result is binarised as described in section 11.4. Missing data for this criterion will be imputed as described in section 6.3.6 for these analyses.

Analysis

The proportion of participants with an IGA score of 0 or 1 at the visit 9 will be compared between Arm A and Arm B using a two-sided stratified CMH test controlling for that factor on which the randomization is stratified, based on the general association statistic (13,14), and performed at the type I error significance level of 0.05. The null hypothesis H_0 is that proportion of participants with an IGA score of 0 or 1 of Arm B. The alternative hypothesis H_a is that proportion of participants with an IGA score of 0 or 1 of Arm A differs from proportion of participants with an IGA score of 0 or 1 of Arm A differs from proportion of participants with an IGA score of 0 or 1 of Arm B.

Let p_{As} be the underlying proportion of responders of Arm A and p_{Bs} be the underlying proportion of responders of Arm B, the null and alternative hypotheses to be tested are as follows:

 H_0 (null hypothesis): $p_{As} = p_{Bs}$

 H_a (alternative hypothesis): $p_{As} \neq p_{Bs}$

Treatment effect will be presented by the common odds ratio (adjusted odds ratio), then in the case where this odds ratio differs by stratum (if the test of homogeneity of odds ratio is significant with a p-value<0.05), by the odds ratio per stratum. These odds ratio will be given with their CI95% calculated by the exact method.

Point estimate of the proportion of participants with an IGA score of 0 or 1 in each arm, computed using the binomial proportion (maximum likelihood estimate for one-way tables), will also be provided along with the corresponding two-sided 95% exact Clopper-Pearson CI (15). In the case where these results differ by stratum, they will also be provided by randomization stratum.

These data will be presented in a table such as the one below:

	Placebo arm	95% CI	Dupilumab arm	95% CI
IGA at the visit 9				
n/missing	n/na		n/na	
Clearance or almost clearance	n (%)	(CI%; CI%)	n (%)	(CI%; CI%)
From mild to severe	n (%)	(CI%; CI%)	n (%)	(CI%; CI%)
Common Odds ratio Control arm to Experimental arm		OR (95%	6 CI)	
Two-sided CMH test	p			

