13.2.2. Eczema area and severity index

Definition and derivation

The efficacy endpoint is the change in EASI score from baseline to Week 16 (quantitative parameter). It is calculated as follows:

EASI score at visit 9 – EASI score at visit 1

Missing data for this criterion will be imputed as described in section 6.3.6 for these analyses.

The change in EASI score from baseline to Week 16 is also expressed as a percentage. It is calculated as follows:

$$\frac{\text{EASI score at visit 9} - \text{EASI score at visit 1}}{\text{EASI score at visit 1}} \times 100$$

It is then binarised in two ways according to this percentage:

- Percentage of improvement greater than or equal to 75% (qualitative parameter: "Yes", "No")
- Percentage of improvement greater than or equal to 90% (qualitative parameter: "Yes", "No")

Analysis

This analysis will be performed only on participants with eczema on a part of the body other than the hands, information collected during the baseline disease assessment (Eczema away from the hands (qualitative parameter: "Yes", "No")).

Change in EASI score from baseline to last visit will be compared between Arm A and Arm B using an ANCOVA with an analysis similar to the primary endpoint.

The proportion of participants with a percentage of improvement greater than or equal to 75% or 90 % at the visit 9 will be compared between Arm A and Arm B using a two-sided stratified CMH test controlling for that factor on which the randomization is stratified. This analysis will be similar to the previous IGA analysis.

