13.2.3. Dermatology life quality index

Definition and derivation

The efficacy endpoint is the change in DLQI score from baseline to Week 16 (quantitative parameter). It is calculated as follows:

Missing data for this criterion will be imputed as described in section 6.3.6 for these analyses.

This score is then binarised according to the improvement from baseline, separating participants with an improvement of 4 or more from the others (qualitative parameter), which corresponds to the Minimal Clinically Important Difference (MCID) of the DLQI (16).

The DLQI score at the visit 9 is also used in binary form as described in section 11.6.

Analyses

Change in DLQI score from baseline to the visit 9 will be compared between Arm A and Arm B using an ANCOVA with an analysis similar to the primary endpoint.

The proportion of participants with an improvement of 4 or more at the visit 9 and the participants with a DLQI score of 0 or 1 at the visit 9 will be compared between Arm A and Arm B using a two-sided stratified CMH test controlling for that factor on which the randomization is stratified. These analyses will be similar to the previous IGA analysis.

13.2.4. 5-Level EQ-5D

Definition and derivation

The EQ-5D-5L questionnaire consists of two parts. The first with qualitative data, the second (EQ-VAS) with quantitative data.

On the first part, the 5 components of the EQ5D-5L will be evaluated for each component by comparing the changes between the baseline results and the results at the visit 9 (qualitative parameter). Changes will be categorized in relation to the baseline, as described in the form associated with the questionnaire (2):

- Their health status (for the respective component) is better
- Their health status has worsened
- Their health status remains the same

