13.2.6. Patient's global assessment of disease severity

Definition and derivation

The efficacy endpoint is based on PaGa score at the visit 9. The test result is binarized as described in section 11.9.

Missing data for this criterion will be imputed as described in section 6.3.8 for these analyses.

Analysis

The proportion of participants with a PaGa score of 0 or 1 at the visit 9 will be compared between Arm A and Arm B using a two-sided stratified CMH test controlling for that factor on which the randomization is stratified. This analysis will be similar to the previous IGA analysis.

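### The responder comparisons control for atopic-dermatitis history but omit the baseline value of the same outcome: the planned test is valid, but some precision is given away

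*SAP*

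**What the plan says.** SAP 13.2.1 sets the method for binary endpoints. "The proportion of participants with an IGA score of 0 or 1 at the visit 9 will be compared" between arms "using a two-sided stratified CMH test controlling for that factor on which the randomization is stratified". SAP 5.1 identifies that factor: "The randomization is performed in a stratified manner based on the presence or not of a personal history of atopic dermatitis".

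Five further sections refer back to this analysis, which gives ten comparisons:

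- 13.2.1: IGA 0/1
- 13.2.2: EASI-75 and EASI-90 ("The proportion of participants with a percentage of improvement greater than or equal to 75% or 90 % at the visit 9")
- 13.2.3: DLQI gain of at least 4 ("The proportion of participants with an improvement of 4 or more at the visit 9") and DLQI 0/1
- 13.2.4: overall EQ-5D-5L improvement
- 13.2.6: PaGa 0/1 ("The proportion of participants with a PaGa score of 0 or 1 at the visit 9")
- 13.2.7: VAS responders for pruritus (40), pain (30) and sleep loss (40)

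No baseline value enters any of them, and no baseline-adjusted sensitivity analysis is planned for them.

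The continuous endpoints are handled differently. The primary analysis in 13.1.2 adjusts by "controlling for those factors on which the randomization is stratified and on the value of the baseline endpoint". The other continuous endpoints follow it by reference, for example "Change in DLQI score from baseline to the visit 9 will be compared between Arm A and Arm B using an ANCOVA" in 13.2.3. Their baseline adjustment therefore comes from being modelled on the primary analysis and is not spelled out endpoint by endpoint.

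Sections 11.4-11.7, 11.9 and 11.10 show that IGA, EASI, DLQI, EQ-5D-5L, PaGa and the VAS scores are all recorded at baseline.

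**The concern.** In 13.2.3 the DLQI change is adjusted for baseline, while the responder variable cut from the same score is not, and no reason is given. The SAP's one remark that baseline severity should not matter (5.1) concerns the relative change in mTLSS. It does not extend to absolute-change thresholds, and mTLSS is adjusted for baseline anyway.

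Two things are at stake. A prognostic covariate left out of a binary comparison costs power. And since randomization is not stratified by severity and 94 patients are planned, a chance difference in baseline between arms passes uncorrected into these comparisons. Clearance judged by investigator and by patient is a named secondary objective (section 4), and its between-arm comparison rests on this test alone.

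**Working it through.** **Step 1: the plan's own figure.** SAP 5.3 gives a difference of 25, SD 40, two-sided alpha 0.05 and 42 per arm. Normal approximation: n = 2 × (1.960 + 0.842)² × 40²/25² = 40.2, so 41 per arm. The exact t-test needs 41.2, so 42, with power 80.8%. Then 84/0.9 = 93.3, so 94. The plan's figures reproduce. It states no response rate or power for any responder endpoint, so every input below is an assumption.

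**Step 2: where baseline limits response by definition.** A patient cannot respond with baseline DLQI below 4, pruritus or sleep-loss VAS below 40, or pain VAS below 30. A patient at EQ-5D profile 11111 cannot be classed as better. The inclusion criteria in 5.1 set no minimum on these scales. That covers five of the ten. For IGA, PaGa, EASI-75, EASI-90 and DLQI 0/1, the effect depends on an association the SAP does not give.

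**Step 3: tests compared.** CMH statistic = [Σ(aₖ − n₁ₖm₁ₖ/Nₖ)]² / Σ[n₁ₖn₀ₖm₁ₖm₀ₖ/(Nₖ²(Nₖ−1))], where in stratum k a is the number of dupilumab responders, n the arm sizes, m the responder and non-responder totals and N the size. The planned version has strata by history only. The alternatives are CMH by history × baseline category, and logistic regression on history and baseline with a likelihood-ratio test for arm.

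**Step 4: IGA 0/1.** 42 per arm, 15% v 42%, baseline IGA 3 and 4 split evenly, 3,000 trials. Power (%):

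| Baseline odds ratio | Planned CMH | CMH, history × baseline | Logistic |
|---|---|---|---|
| 1 | 79.7 | 78.6 | 80.5 |
| 2 | 79.8 | 79.8 | 81.6 |
| 3 | 79.9 | 81.2 | 82.9 |
| 5 | 78.9 | 82.4 | 84.3 |

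The logistic gain is 0.8 to 5.4 points. Part of the gain at odds ratio 1 reflects that test's slightly higher size (5.2-5.4%, against 4.7-5.0% for the planned CMH). A second set, with 47 per arm and about 15-17% v 35-37%, gave 69% unchanged (weakly prognostic), 63% to 66% (moderate) and 59% to 67% (strong). Together: about 0-8 points.

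**Step 5: a continuous baseline in general.** 42 per arm, 30% v 60%, odds ratio per baseline SD of 1/1.5/2/3/5. Planned CMH: 78.6/78.4/78.1/81.3/79.5%. Logistic: 80.0/80.6/82.9/88.9/92.1%. Gain: 1.4 to 12.6 points. Null size was 4.6-5.1% for the planned CMH and 5.1-5.7% for the logistic test.

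**Step 6: VAS gain of at least 40.** 42 per arm, baseline SD 25 mm truncated to 0-100 mm, response 25% v 60% among those starting at 40 mm or more and zero below, 4,000 trials:

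| Mean baseline (mm) | Able to respond | Planned CMH | CMH, history × able |
|---|---|---|---|
| 40 | 50% | 50.2% | 62.8% |
| 50 | 66% | 65.6% | 74.4% |
| 60 | 79% | 78.7% | 83.7% |
| 70 | 89% | 84.4% | 87.9% |

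At a mean of 50 mm the overall rates are 0.66 × 25% = 16.5% and 0.66 × 60% = 39.6%. The gain runs from 3.5 to 12.6 points. The 47-per-arm set, at equal test size, gave 44% to 47-49% and 68% to 74-76%. Together: about 3-13 points. For DLQI improvement of 4 or more the same set gave 46% to 46-48% and 51% to 58-61%: about 0-10 points. That range has no second derivation and is indicative.

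**Step 7: chance imbalance.** With 42 per arm the between-arm difference in mean baseline has SD √(2/42) = 0.22 baseline SDs. In the VAS row with 66% able to respond, that share differs between arms with SD √(0.66 × 0.34 × 2/42) = 0.10.

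**The case against.** The CMH test respects the randomization factor and keeps its size. Baseline in an ANCOVA alongside only the stratification factor in a CMH test is a common pairing. SAP 6.2 calls the secondary analyses exploratory with no claims intended, and the trial is sized on the primary endpoint alone, so no power target is missed. Seven of the ten responders (both EASI, both DLQI and the three VAS) sit beside an ANCOVA of the same instrument. All of this stands and limits the weight of the point. It does not remove it: the covariate is already collected, and the three remaining comparisons have no such companion.

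Three stronger readings are tempting and should be resisted.

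- **All ten comparisons lose power.** They need not. With a weakly prognostic baseline the IGA gain was nil, and by inclusion criterion IGA starts at 3 or 4, which leaves little to adjust for.
- **The false-positive rate is near 10%.** Under the null in the VAS case, the planned CMH rejected in 9.6% of trials whose baseline means differed by more than 0.3 SD, against 6.3% for logistic regression with baseline. Those are only 15% of trials. With overall size near 5%, the rest run at about (5 − 0.15 × 9.6)/0.85 = 4.2%.
- **The plan contradicts itself.** It treats two classes of endpoint differently without explanation, but no statement in it is wrong.

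**Conclusion.** The point holds as one of efficiency. The responder comparisons omit a baseline value that the trial collects and uses in its continuous analyses. The planned test is valid, so a reader should not infer bias or an inflated overall error rate, and the primary conclusion is untouched.

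The sizes in the working rest on assumed response rates and assumed strength of baseline. The upper ends need a strongly prognostic baseline, or for VAS a mean baseline close to the threshold. The case is firmest for the five endpoints where low scorers cannot respond, to the extent that such patients are enrolled. The practical gap is widest for IGA, PaGa and EQ-5D improvement, because nothing else in the plan compares those outcomes with baseline taken into account.

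**What to change.** Before unblinding, amend 13.2.1 and the sections that refer to it:

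- Analyse each responder endpoint by logistic regression with arm, atopic-dermatitis history and the baseline value of the same outcome: IGA 3 v 4, PaGa category, or the DLQI, EASI or VAS score. For EQ-5D, define a baseline summary such as the sum of the five levels, since the SAP has a profile but no index score.
- State where any patient with baseline IGA below 3 is placed (8.2.2 foresees them), and add a rule for missing baseline IGA or PaGa, which 6.3.6 lacks.
- Use a penalised likelihood where responders are few, as in the EASI subset. At 15% of 47, placebo IGA responders would number about 7.
- Report the adjusted odds ratio and the standardised risk difference, each with a 95% CI.
- Keep the planned CMH as a sensitivity analysis, and keep the homogeneity test and per-stratum odds ratios on atopic-dermatitis history only.

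Regression is preferable to a finer CMH. History × baseline tertiles makes six strata, about 47/6 ≈ 8 patients per arm each if evenly filled, and the per-stratum rule in 13.2.1 would then act on very sparse tables.

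The cost is SAP wording and a few lines of code, with no new data. The downsides are a model-based test that may be slightly liberal at this size (about 5-6%) and an odds ratio that is conditional on baseline, which is why the standardised risk difference should accompany it.
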